**Table 1: Comparison of BED in Different Fractionation Schedules**

|                          | Total dose | # of Fractions | Dose per fraction (Gy) | alpha/beta | BED |
|--------------------------|------------|----------------|------------------------|------------|-----|
| Early Responding Tissues | 30         | 10             | 3                      | 10         | 39  |
|                          | 20         | 5              | 4                      | 10         | 28  |
|                          | 24         | 3              | 8                      | 10         | 43  |
| Late Responding Tissues  | 30         | 10             | 3                      | 3          | 60  |
|                          | 20         | 5              | 4                      | 3          | 47  |
|                          | 24         | 3              | 8                      | 3          | 88  |

[figure not shown]
### 1.3.5 STAT RT: A Rapid Palliative Radiotherapy Workflow

The University of Virginia Radiation Oncology Department has received institutional funding through an institutional Buchanan Grant and a CMS Innovation Award to fund the technical development of a TomoTherapy-based STAT RT program for rapid pain palliation. We have already treated over 30 patients in the first phase of development of this program with a STAT RT workflow that compresses the standard workflow to 6 hours allowing same day simulation, treatment planning, and treatment delivery. In the second phase of development we will optimize the combination of several recent computing advancements to create a Scan-Plan-Treat STAT RT workflow in which CT simulation, treatment planning, and treatment delivery with real time quality assurance will be performed on a single system in approximately 30 minutes.

### 1.3.6 Technologic Rationale For The Choice of The TomoTherapy Platform

TomoTherapy delivers highly conformal and homogenous dose distributions through modulation of dose from a bank of 64 binary 6.25-mm-wide collimator leaves capable of pneumatic opening or closing 51 times per revolution as the gantry revolves around the patient **See Figure 3**. The system can also treat patients with discrete beam angles (i.e. the radiation beam not rotating) in a mode called TomoDirect. Due to increased costs for IMRT, this treatment technique is not allowable for the treatment of non-spine bone metastases. Although all TomoTherapy treatment delivery is technically IMRT, the treatment planning can be done in either a 3D or IMRT mode allowing highly conformal treatments to be billed as 3D and thus used in the treatment of all patients with bone metastases. In addition, good preliminary data exists to support the use of the fan beam MVCT as a CT simulation image set for treatment planning and the use of CT detector-based exit dose methodology for quality assurance, making this system an excellent platform to pilot this research.

**Figure 3: Helical TomoTherapy Unit**

### **1.3.7 STAT RT Workflow: Same Day CT Simulation, Treatment Planning, Treatment Delivery**

As previously stated, we have already developed a STAT RT workflow for same day palliation that requires approximately 6 hours, and is a highly coordinated conventional workflow with kVCT simulation, treatment planning, treatment plan quality assurance, and then delivery of conformal hypofractionated radiotherapy. All treatments are planned and delivered on FDA-approved systems. We have treated over 30 patients to date with this workflow, and preliminary results reveal rapid and durable palliation with minimal acute toxicity. This workflow allows patients to receive an entire course of palliative treatment from start to finish in 1 to 5 days, a process that conventionally takes 3 weeks. Since patients are billed for each individual treatment, requiring fewer treatments reduces health care costs in addition to being more convenient. With the STAT RT program we are now able to offer a unique workflow that delivers rapid, effective, and efficient palliative radiotherapy that is cost effective, less toxic, and more convenient for cancer patients and their families. The dose conformality of these treatments is excellent and will not be further optimized. In this pilot clinical trial, for the primary specific aim we will quantify patient outcomes following treatment with the current STAT RT workflow in an effort to determine its benefits and risks to patients. As a secondary aim, we will systematically evaluate and optimize the software necessary for the clinical implementation of the more efficient Scan-Plan-Treat STAT RT workflow.

### **1.3.8 Scan-Plan-Treat STAT RT Workflow: A Novel and More Efficient STAT RT Workflow**

With recent advances in software and technology, we plan to further condense the STAT RT workflow into the Scan-Plan-Treat workflow, a 30-minute process in which all steps (MVCT simulation, diagnostic image co-registration, treatment planning, and treatment delivery with real time quality assurance) are performed on the TomoTherapy unit. This advanced workflow will eliminate the need for the patients to undergo a kvCT simulation on a separate unit as well as make it unnecessary for the patient to leave the treatment table between the simulation and treatment.

### **1.3.9 Secondary Aims: Requirements For Clinical Implementation of the Scan-Plan-Treat STAT RT Workflow**

- 1) MVCT simulation image acquisition (10 minutes) then rigid or deformable image co-registration of existing diagnostic image sets with pre-contoured target and OAR volumes to the MVCT simulation scan for contour transfer (3-5 minutes).**
- 2) Rapid inverse treatment planning (3-5 minutes).**
- 3) Monte Carlo secondary dose calculation (2-3 min)**
- 4) At the Emily Couric Cancer Center location, simple real-time patient motion tracking via infrared cameras to ensure accurate patient setup during MVCT**

simulation and treatment delivery (concurrent). No data for this aim will be collected at CRH.

[figure not shown]
- 5) Patient-specific quality assurance using CT detectors during treatment delivery (10 minutes).

### **1. New image co-registration workflow**

In the conventional workflow, target volumes and OARs are contoured on recent diagnostic images (MRI, PET-CT, or diagnostic CT that are already available in the patient's electronic radiology chart). After the patient undergoes a kVCT simulation, the contoured diagnostic images are rigidly or deformably co-registered to the kVCT simulation images, and the contours are transferred. This allows for high resolution diagnostic images to be used for tumor and normal tissue identification, which is not always possible to differentiate on CT simulation scans due to the resolution of standard wide bore CT simulation scanners. Multiple commercial image processing systems are available for this image processing, and we are currently using Velocity® (Atlanta, GA) image processing software. Following treatment planning, the patient then undergoes image guided treatment delivery, a process in which a daily MVCT scan is obtained on the TomoTherapy unit and co-registered to the planning kVCT scan. Patient setup shifts can then be made to ensure accurate patient setup, and the patient is treated. Therefore, this is a two image co-registration workflow. See **Figure 4**.

A kVCT simulation scan has historically been used for simulation in the conventional workflow for both palliative and curative radiation planning. Compared to MVCT scans, it has higher resolution and allows the possibility for administration of iodinated IV and/or GI contrast, which makes it easier to identify soft tissues and bony anatomy for treatment planning. However, contrast agents are not generally given for kVCT simulations of patients for palliative treatment of osseous metastases since the soft tissue and bone windows are adequate. MVCT scan soft tissue and bone windows have quite reasonable resolution and can easily be co-registered to higher resolution diagnostic studies for contour transfer. MVCT scans are routinely co-registered to kVCT scans for image guidance on a daily basis. Our preliminary data suggests that the optimization of this one step image co-registration workflow of diagnostic image sets to a MVCT simulation scan is clinically similar to the conventional two image co-registration workflow.

**Figure 4: Comparison of Image Co-Registration Workflows**

## 2. Rapid inverse treatment planning on MVCT scans

CT image sets are used for radiation treatment planning because the electron density of tissues, which is required for calculating dose, is easily determined based on the Hounsfield units. The tissue electron density determination is essentially the same for MVCT and kVCT scans. It has previously been reported that as far as the dose calculations are concerned, treatment planning on either a kVCT simulation image set or an MVCT simulation image set yields treatment plans that are within 1% of each other(38).

We have recently published that the TomoTherapy STAT RT treatment planning module can calculate SBRT and palliative treatment plans in just a few minutes(39). The computing speed of radiation treatment planning systems is about to take a quantum leap forward with the incorporation of new algorithms that will take advantage of the replacement of central processing units with graphic processing unit's whose more rapid and parallel calculating potential can improve treatment planning speed by 10-20 times(40, 41). Real time inverse treatment planning of IMRT or 3D TomoTherapy plans has not been a problem for patients treated with STAT RT to date. We will compare planning times for current FDA-approved treatment planning systems as well as for newer, in-development GPU-based algorithms.

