**b) Rapid inverse treatment planning on MVCT scans**

We have shown that accelerated treatment planning software for Helical TomoTherapy provides clinically acceptable dosimetry, with conformality and homogeneity that is superior to standard LINAC-based 3D conformal planning and is only slightly inferior to standard Helical TomoTherapy dosimetry (33). We have also shown that, with planning times of 2-5 minutes, this accelerated treatment planning software provides levels of dosimetric conformality, heterogeneity, and avoidance of organs at risk for simple SBRT treatments that are clinically equivalent to those generated with conventional Helical TomoTherapy treatment planning(39). This preliminary data supports that treatment planning speed is not likely to be rate limiting in the ultimate clinical implementation of the Scan-Plan-Treat STAT RT workflow.

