**b) Treatment Planning Speeds**

We will determine the speed of radiation treatment planning with our current clinical system and compare this to the speed of planning with newer in-development algorithms running on next generation computers with graphic processing units (GPUs). Since highly conformal radiation treatments must be routinely calculated in a few minutes for the Scan-Plan-Treat STAT RT workflow, we will determine if the treatment planning with GPUs is fast enough for clinical implementation (i.e. can be done in approximately 5 minutes). If not, we will optimize the planning process in collaboration with TomoTherapy, Inc to increase the speed of planning.

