Contours generated from the conventional and experimental image registration flows will be compared in a variety of ways as described in Section 7.1. All comparisons of the contouring measures, including the Dice indices, will be performed using paired two-sample t-tests.

Toxicity will be recorded using CTCAE 4.0 criteria and RTOG Late Radiation Morbidity Scoring Criteria. The incidences of grade 3 or more toxicities will be reported.

The effectiveness of the infrared tracking system will be determined by comparing its position calculations with the position of the patient as determined by the position of the lasers with respect to the set up skin marks before and after treatment. The position changes calculated by each method will be compared using paired two-sample t-tests.

The average treatment planning speed of radiation treatment planning with our current clinical system will be calculated and compared the average speed of planning with newer in-development algorithms running on next generation computers with graphic processing units. These means will be compared with two-sample t-tests.

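### No dosimetric condition is stated for the timed GPU treatment plans, so the planning-speed result cannot show that a usable plan was produced in the time

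*Combined protocol and SAP*

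**What the plan says.** Three places describe the planning comparison.

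- Section 1.3.9, item 2: "We will compare planning times for current FDA-approved treatment planning systems as well as for newer, in-development GPU-based algorithms".
- Section 7.1, secondary aim b (Treatment Planning Speeds): "we will determine if the treatment planning with GPUs is fast enough for clinical implementation (i.e. can be done in approximately 5 minutes". The response to failure is also about time: "If not, we will optimize the planning process in collaboration with TomoTherapy, Inc to increase the speed of planning".
- Section 7.3: "The average treatment planning speed of radiation treatment planning with our current clinical system will be calculated" and set against the average for the GPU-based algorithms. "These means will be compared with two-sample t-tests".

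The background on existing accelerated software is in Section 1.4, item 2b, which reports two separate comparisons with conventional Helical TomoTherapy planning. In one, accelerated dosimetry is called clinically acceptable and better than LINAC-based 3D conformal planning, and it "is only slightly inferior to standard Helical TomoTherapy dosimetry (33". No planning time is attached to that result. The other covers simple SBRT treatments, "with planning times of 2-5 minutes", and reports clinically equivalent conformality, heterogeneity and organ avoidance. The section concludes that planning speed is unlikely to limit the future workflow.

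**The concern.** A planning time can be interpreted only together with the plan it produced. The secondary hypothesis in Section 1.1 is that the new components will be effective as well as efficient, treatment planning included. Timing addresses efficiency only. Conformality is also the main argument for the technique in Sections 1.2.2 and 1.3.

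At stake is the decision in Section 7.1b: accept GPU planning as fast enough, or work on it further. On the stated criterion, a GPU plan finished within about 5 minutes meets the target whether or not it meets the coverage and organ limits required of a treatment plan. The report would then give a time with no evidence about what was achieved in it.

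**Working it through.** The plan gives no figure for this comparison to reproduce. Its only sample-size calculation (21 patients, for BPI pain, in Section 7.2) does not bear on it. The check is mainly a reading, with a little arithmetic for the paired analysis.

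**1. Is plan quality assessed anywhere for the GPU plans?**

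| Place | What it covers | Closes the gap? |
|---|---|---|
| 7.1b, 7.3 and 1.3.9 item 2 | Planning time | No |
| 1.3.9 item 3, Monte Carlo second check | Accuracy of the dose calculation | No. An accurately calculated plan can still be less conformal, and inclusion of the GPU research plans is not stated |
| 4.2, dosimetry form | PTV and organ criteria for each study subject | Not as written. It is not tied to the research plans |
| 4.2 and 7.1c, phantom QA and exit dose | Delivered against planned dose | No |

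**2. How do the neighbouring secondary aims compare?** Co-registration has an acceptability threshold (Dice index of 0.8 or higher). Exit-dose verification has a target (within 3%). Motion tracking has an anticipated accuracy (2-3 mm). Planning has a time only.

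**3. How much can the time criterion discriminate?** The target is about 5 minutes. Existing accelerated software is already reported at 2-5 minutes for simple SBRT. The reported range lies within the target, so for cases of that kind the criterion may separate little. Whether this carries over to the trial's cases, with 1-3 target lesions each, is not stated.

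**4. What does pairing change?** Section 7.3 specifies two-sample t-tests. The plan does not say whether the same cases are planned on both systems; assume they are, for all 30 patients. Let σ be the SD of planning time on each system and ρ the within-case correlation.

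- Two-sample t-test, 30 per group, two-sided 0.05, 80% power: detectable difference 0.736σ.
- Paired t-test, 30 pairs, same error rates: detectable difference 0.53 × SD of the paired difference, where that SD = σ√(2(1 − ρ)).
  - ρ = 0: 0.53 × 1.414σ = 0.75σ
  - ρ = 0.5: 0.53 × 1.000σ = 0.53σ
  - ρ = 0.8: 0.53 × 0.632σ = 0.34σ

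The documents do not give ρ; 0 to 0.8 is an assumed range. If harder cases take longer on both systems, ρ is positive and the unpaired test wastes information.

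**5. Could plan quality be compared formally with 30 patients?** The documents give no dosimetric margin or SD, so the margin is expressed in SDs of the paired difference. For a paired non-inferiority test (one-sided 0.025, 80% power, true difference zero), 30 patients support a margin of about 0.53 SD and 21 patients about 0.64 SD. Margins of 0.25, 0.5 and 1.0 SD need 128, 34 and 10 patients. Descriptive reporting needs no extra patients.

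**The case against.** The best defence is that Section 7.1b asks a limited question. Being fast enough is a necessary condition for clinical use, and nothing says it is sufficient. The same sentence refers to highly conformal treatments, so adequate quality is taken for granted. Planning speed is also peripheral: it is absent from the secondary objectives in Section 2.2 and from aims A to C in the synopsis. Section 7.1 says these components are not used in direct patient care, and Section 1.4 says the Scan-Plan-Treat workflow is not used on this protocol. All of this stands, and it limits the weight of the point. It does not supply the missing condition, because quality is presumed for the timed plans and never checked.

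A reader might infer four stronger things, none of which the documents support.

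- *That a fast but worse plan would be adopted.* No section makes the time target sufficient for adoption.
- *That accelerated planning gained speed by losing quality.* The 2-5 minute result belongs to the comparison reported as equivalent. The slightly inferior result was still called clinically acceptable and carries no time.
- *That GPU planning would take seconds.* Applying the quoted 10-20 fold gain to 2-5 minutes gives 120 s/20 = 6 s to 300 s/10 = 30 s. Section 1.3.9 gives no baseline for that gain, and the titles of the two cited papers refer to dose calculation, which need not be the whole planning process.
- *That GPU software would be quick because it stops optimising early.* Section 1.3.9 attributes the expected speed to faster, parallel computation.

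**Conclusion.** The gap is real but modest. For the in-development GPU algorithms the plan measures time only, states no dosimetric condition and presents no dosimetric data. A result of about 5 minutes therefore cannot show that a clinically usable plan was produced in that time. The 2-5 minutes already reported for simple SBRT suggests that time alone may discriminate little. How little cannot be stated, because the GPU gain over that baseline is not given.

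The consequence is confined to interpreting an ancillary secondary measurement and to decisions about a future workflow. The primary aim and the treatment of trial patients are untouched. The advantage of pairing rests on the assumption that the same cases are, or can be, planned on both systems.

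**What to change.** In Sections 7.1b and 7.3:

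1. Plan each case on both systems with the same image set, contours and prescription.
2. Count a GPU plan as meeting the time target only if it also meets the PTV and organ criteria already on the Section 4.2 dosimetry form, completed for the research plan.
3. Report paired differences in PTV coverage, conformality and homogeneity beside the paired planning times.
4. Replace the two-sample t-test with a paired analysis.

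Formal non-inferiority is optional. If it is wanted, the margin should be prespecified and justified, bearing in mind that 30 patients support only margins of about 0.53 SD or wider.

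The cost is revised wording and modest extra evaluation per research plan, assuming the in-development software exports dose-volume data, which the documents do not confirm. The reported success rate may be lower. No visits, patients or changes to treatment are needed.

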### **3. Fast Monte Carlo based secondary dose calculation**

Most treatments delivered on a traditional linear accelerator undergo a secondary dose calculation before the patient is treated. The secondary calculation is compared to the dose calculated by the treatment planning system and must be within agreement before the treatment can be administered. With the addition of [name] to the research team, UVa now has access to a very fast secondary dose calculation algorithm specifically designed for TomoTherapy. Using this Monte Carlo based software, all treatment plans will be second checked for dose calculation accuracy.

### **4. Optical tracking methods for patient intra-fractional motion monitoring**

Consistent patient positioning during CT image acquisition and treatment is critical to ensure accurate dose delivery. Physical immobilization devices such as external body frames, aquaplast masks and other body molds, and vac-lock vacuum bags are commonly used to ensure patient positioning reproducibility. X-ray or CT image guidance prior to radiation delivery on the treatment unit is routinely employed in the clinic. Methods for optical tracking of markers on the patient surface or of the patient's skin surface are available to ensure consistent patient positioning after image guidance and during treatment, known as intra-fractional motion (42, 43). This provides a method without ionizing radiation for confirming patient position that can be used real time during the treatment process. With this information, treatment can be paused if the patient's position changes during treatment. At the Emily Couric Cancer Center, we have developed an inexpensive in-house optical tracking system to monitor patient positioning real time that we will optimize in this protocol. Culpeper Regional Hospital does not have this imaging capability and patients treated on this protocol at CRH will not have optical surface tracking.

### **5. Novel CT-detector-based quality assurance methodology**

Current standard of care TomoTherapy quality assurance methodology requires that each patient-specific treatment plan be delivered to a cylindrical plastic phantom with ion chamber and film measurement or an array of radiation detectors to ensure geometric and dose accuracy to within  $\pm 3\%$ . However, this method does not measure the dose that the patient is receiving during treatment or provide full 3D dose verification. It causes another delay in delivering the first treatment to the patient as it requires approximately 30-40 minutes to complete, and is generally done by a medical physicist after clinical patient care is finished. A methodology to monitor the patient exit dose in real time would increase patient safety through verification of daily treatment accuracy as well as expedite the treatment workflow. Clearly, a real-time quality assurance methodology that does not require moving the patient off the TomoTherapy treatment couch for phantom measurements is essential for the development of a 30-minute Scan-Plan-Treat workflow. Current dose verification methodologies measuring dose at the time of patient treatment are limited to point measurements on the patient surface (44), which is rarely in the target volume or a critical OAR, or though

expensive implanted dosimeters (45, 46) which are not practical for most palliative patients. Since there is not a method to directly measure the three dimensional dose in the patient, alternative approaches are being developed and tested in academic clinical settings. These alternative approaches reconstruct the delivered three dimensional dose distribution based on the measurement of either entrance or exit dose and back-projecting the measurements onto simulation or image guidance CT image sets.

The opportunity to reconstruct dose from information collected during treatment became available with the incorporation of radiation imaging detectors, such as electronic portal imaging devices (EPID) on linear-accelerators and CT detector arrays on TomoTherapy. Dose reconstruction using in-line EPID was first described by McNutt et al (47, 48). The EPID, when deployed during treatment, collects exit fluence from the patient and then back-projects this to X-ray fluence before entering the patient; then, the dose in the patient is re-computed using this entrance fluence and the planning CT images. However, there are many limitations to EPID-based dose verification. For example, the EPID was originally designed for semi-quantitative portal imaging; and for the purpose of dose reconstruction, it suffers from a narrow dynamic range, short life span, non-linearity in the dose response, ghost artifacts from low temporal resolution, and cross-plane scatter photon contribution to the measured fluence (49). Investigators are currently working on methods to overcome these challenges.

The TomoTherapy unit has an in-line source-patient-detector geometry with CT ion chamber detectors that are used for daily MVCT scan image guidance for accurate patient positioning that remain in place during both imaging and treatment. **See Figure 3**. These CT detectors can also be used to measure the patient exit dose fluence and back-project this onto a planning CT scan for volumetric or 3D dose reconstruction. Dose verification on TomoTherapy was first studied by Kapatoes et al., who calculated the entrance fluence from the exit dose using a transfer matrix, which is calculated based on the radiological path length from the source to the detector (50, 51). The use of a CT ion chamber array has multiple advantages over EPID for exit fluence measurement. It is more durable, and has a much longer life span. It has a wider dynamic range and doesn't limit treatment positions. Finally, it is less sensitive to the noise from cross-plane scatter photons that complicate EPID-based dose reconstruction (52). Our recently published preliminary data showed that the current TomoTherapy CT-detector based algorithm for dose reconstruction is robust with +/- 3-5% accuracy which is well within the acceptable range for clinical care (53). We will collect clinical data and continue to optimize this in-development software.

One drawback from the dose reconstruction method mentioned above is that it relies on the accurate knowledge of the patient geometry and attenuation at the time of the treatment. This information may not be fully available nor accurate. This leads to the ambiguity in determining whether a discrepancy observed from the dose reconstruction is real (caused by the machine) or merely an artifact caused by the patient such as weight loss or

positional changes. To remedy this, we have developed a method to detect if the multi-leaf collimator (MLC) is open or close based on the sharp change in the exit fluence independent of the patient attenuation (54). In addition, the LINAC output and gantry angles during treatment are measured independently for quality assurance. Combining those data, the impact of deviations during the treatment delivery can be evaluated through the MCL dose calculation. The CT detector clinical data collected will also be used to optimize this in-development software.

